### 7.3 Handling of efficacy endpoints if rescue therapy is performed

If rescue therapy is performed, data from the day after rescue therapy should not be used to assess efficacy.

### 7.4 Imputation of missing values

The mixed model repeated measures (hereinafter, MMRM) should not use data imputing missing data. If there are missing values at the first day of the treatment period, data from the day closest to the first day of the treatment period should be used as data for the first day of the treatment period.

In the case of missing data in calculating descriptive statistics of mean Hb values at Weeks 48 and 52 of the treatment period, missing data should be imputed with data from the evaluation time point immediately before the missing evaluation time point (excluding the first day of the treatment period) (hereinafter, LOCF method). When any one evaluation time points has missing values, the data at the evaluation time point closest to the missing evaluation time point is adopted, and when two evaluation time points have missing values, the data in the two different evaluation time points closest to and before the missing evaluation time points should be adopted to calculate the mean Hb value. However, Hb values at the same evaluation time point should not be used.

In addition, values imputed by the LOCF method at Week 52 of the treatment period should also be derived for clinical laboratory value, vital sign, QOL indices among the efficacy endpoints.

## 7.5 Handling of clinical laboratory test values less than the limit of quantification

If the measured values are reported to be not more than the limit of quantification, less than the limit of quantification, or impossible to calculate, the following handling procedures should be applied for tabulation, and missing values or zero values should not be used.

[Handling of quantification limit values]

- (1) If the measurement is reported as less than the limit of quantification

The value obtained by adding the following processing to the quantification limit value is used as an alternative value for tabulation.

- 1) After checking the number of significant figures of the applicable item, 1 should be subtracted from the significant figure of the lowest reported quantification limit value.
- 2) It should then be expanded by one digit to a smaller number and 9 is set.

Example) Report: < 3 Significant figures of the measuring facility: up to ones digit  
→ Tabulation handling: 2.9

Report: <500 Significant figures of the measuring facility: up to tens digit  
→ Tabulation handling: 499

- (2) When the measured value is reported as not more than the limit of quantification or not less than the upper limit of quantification, the limit of quantification itself should be used as a substitute value for tabulation.

Example) Not more than the limit of quantification

Report:  $\leq 10$  → Tabulation handling: 10

Not less than the limit of quantification

Report:  $\geq 20$  → Tabulation handling: 20

## 8. Statistical Method

In this trial, when the observation of all subjects is completed, the final data will be fixed, and the statistical analysis should be conducted.

### 8.1 Basic matters

#### 8.1.1 Level of significance and confidence coefficient

When implementing tests, level of significance should be set at 2-sided 5%. Confidence interval will be 2-sided with a confidence coefficient of 95%.

### 8.1.2 Descriptive statistics to calculate

Types of descriptive statistics items to be calculated for each continuous variable are provided below.

Number of subjects, mean, standard deviation (SD), median, minimum, maximum, and 2-sided 95% CI of the mean.

### 8.1.3 Number of digits displayed

The number of digits to be displayed in the analysis results will be as follows.

Numeric content	Number of display digits
p value	3 decimal places; however, when it is less than 0.001, it is described as “< 0.001”
Proportion (percentage)	Integer part + 1 decimal place
Rate of change	Integer part + 1 decimal place
Descriptive statistics (minimum and maximum)	Same as the number of digits as original variable
Descriptive statistics (mean, SD, median)	Number of digits of the original variable + 1 digit
Rate of increase in Hb value	Integer part + 4 decimal places
QOL (EQ-5D-5L) index value	Integer part + 3 decimal places

Hepcidin will be measured in units of pg/mL; however, the unit used for tabulation should be ng/mL, and the number of displayed digits should be two decimal places.

## 8.2 Breakdown of subjects

### 8.2.1 Disposition

For subjects enrolled in the treatment period, the breakdown of each analysis set in each treatment group should be provided.

Items: Number of subjects enrolled in treatment period, number of subjects completed the treatment period phase 2, number of subjects discontinued the study, number of subjects who received rescue therapy, number of subjects in the FAS and its proportion, number of subjects not included in the FAS and its proportion, number of subjects and its proportion in the safety analysis set, number of subjects not included in the safety analysis set and its proportion

### 8.2.2 Subjects who discontinued or interrupted their treatment

For subjects enrolled in the treatment period, the number and proportion of discontinued subjects should be tabulated in each treatment group and by reasons for discontinuation. Subjects who entered

specific comments ("Criterion for liver function") according to the input rules should be counted for the number of subjects discontinued by reasons that meet the discontinuation criteria for abnormal hepatic function values.

Items: Number and proportion of subjects who discontinued in each treatment group among those enrolled in the treatment period; number and proportion subjects who discontinued by reasons

In addition, for subjects enrolled in the treatment period, the number and proportion of discontinued subjects should be tabulated in each treatment group and in every 12 weeks (tabulation unit: from first day of the treatment period (Day 1) to Day 84, Days 85–168, Days 169–252, and Day 253 and onward.

Item: Number and proportion of subjects who discontinued in each treatment group among those enrolled in the treatment period

For subjects enrolled in the treatment period, the number of cases of interruption of MT-6548 tablets 150 mg in the MT-6548 group and darbepoetin alfa injection (recombinant) in the darbepoetin group should be tabulated by reasons for drug interruptions. The denominator of the proportion should be the sum of the number of drug interruptions. If there are multiple reasons for a single interruption, it should be counted for each reason and tabulated as the total number of interruption cases. For drug interruption due to abnormal hepatic function, subjects who entered specific comments according to the input rules ("Criterion for liver function") should be tabulated.

Items: Number of cases of interruption of MT-6548 tablets 150 mg/darbepoetin alfa injection in each treatment group among subjects enrolled in the treatment group; number and proportion of cases of interruptions by reasons

### 8.3 Demographic and other baseline characteristics

For each analysis set, the key demographic and other baseline characteristics for each treatment group should be summarized. Frequency and proportion will be provided for discrete variables and descriptive statistics for continuous variables (no calculation of 95% CI of the mean).

Table 8.3.1 Items relating to demographic and other baseline characteristics

Category	Item	Type of variables
Subject background	Sex (male, female)	Dichotomous
	Age (years) as of informed consent	Continuous

Confidential

	2 categories: <65, ≥65	Dichotomous
	2 categories: <75, ≥75	Dichotomous
	Duration of nephrogenic anemia (years)	Continuous
	3 categories: <1, 1 to <5, ≥5	Ordinal
	Height (cm)	Continuous
	Dry weight (kg)	Continuous
	BMI (kg/m  )	Continuous
	2 categories: <25, ≥25	Dichotomous
	Race	
	3 categories: not Hispanic or Latino, Hispanic or Latino, Unknown	Polytomous
	Ethnicity	
	3 categories: Asian (Japanese), Asian (Other), other	Polytomous
Smoking status	Presence or absence of smoking status 3 categories: never smoked, ex-smoker, current smoker	Polytomous
Underlying cause of CKD	Underlying cause 8 categories: diabetes mellitus, hypertension, autoimmune/glomerulonephritis/vasculitis, interstitial nephritis/pyelonephritis, cystic/hereditary/congenital disease, neoplasm/tumor, unknown, other	Polytomous
Complication	Presence or absence of complications on the first day of the treatment period	Dichotomous
	Presence or absence of hypertension	Dichotomous
	Presence or absence of diabetes mellitus	Dichotomous
	Presence or absence of dyslipidemia	Dichotomous
Previous ESA formulation	Type of previous ESA formulation 4 categories: epoetin (epoetin alfa, epoetin beta, or epoetin kappa), darbepoetin alfa, epoetin beta pegol, other	Polytomous
	Frequency of administration by type of previous ESA formulation 7 categories: once a week, twice a week, three times a week, every 2 weeks, every 3 weeks, every 4 weeks, other	Polytomous
	Weekly dose of epoetin alfa, epoetin beta, or epoetin kappa (IU)	Continuous
	Weekly dose of darbepoetin alfa (μg)	Continuous
	Weekly dose of epoetin beta pegol (μg)	Continuous
	Hb value (g/dL) on the first day of the treatment period 3 categories: <10, 10 to <11, ≥11	Continuous
Evaluation data	3 categories: <10, 10 to <11, ≥11	Tricotomous
	Liver function test (U/L) on the first day of the treatment period	
	3 categories: AST and ALT are both not more than the upper limit of normal, either is more than the upper limit of normal and both are not more than 2 times the upper limit of normal, either is more than 2 times the upper limit of normal	Tricotomous
	CRP (mg/dL) on the first day of the treatment period	Continuous
	Serum ferritin (ng/mL) on the first day of the treatment period	Continuous
	2 categories: <100, ≥100	Dichotomous
	TSAT (%) on the first day of the treatment period	Continuous
	2 categories: <20, ≥20	Dichotomous
	With or without iron supplements on the first day of the treatment period	Dichotomous
	2 categories: oral, intravenous	Dichotomous

	With or without iron-containing phosphate binders on the first day of the treatment period	Dichotomous
Hemodialysis	Types of hemodialysis (2 categories: hemodialysis, hemodiafiltration)	Dichotomous
	Duration of hemodialysis (years)	Continuous
	Frequency of dialysis (2 categories: 3x per week, other)	Dichotomous

## 8.4 Study drug administration/treatment period and compliance status

For FAS and safety analysis set, the descriptive statistics of administration/compliance rate (no calculation of 95% CI of the mean) of MT-6548 tablets 150 mg/darbepoetin alfa injection (recombinant) should be calculated by treatment group to provide the number and proportion of subjects with administration/compliance rate of MT-6548 tablets 150 mg/darbepoetin alfa injection (recombinant) of  $\geq 80\%$  and  $< 80\%$ .

For FAS and safety analysis set, the descriptive statistics of the study drug administration/treatment period (no calculation of 95% CI of the mean) should be calculated by treatment group.

For FAS and safety analysis set, the descriptive statistics of the cumulative dosage of MT-6548 tablets 150 mg/darbepoetin alfa injection (recombinant) should be calculated by treatment group (no calculation of 95% CI of the mean).

## 8.5 Efficacy analysis

As a general rule, efficacy analysis will be performed on the FAS. When necessary, descriptive statistics for continuous variables should be calculated and frequency and proportion will be calculated for discrete variables. No data from the day after the rescue therapy implementation date should be included in the efficacy analysis.

### 8.5.1 Analysis of secondary endpoints

#### (1) Mean Hb values at Week 48 and Week 52 of the treatment period

Descriptive statistics for changes in Hb values from the first day of the treatment period to mean Hb values at Week 48 and Week 52 in the treatment period should be calculated for each treatment group. The MMRM is used to model the mean Hb values at each evaluation time point based on the following model, and the mean Hb values at Week 48 and Week 52 of the treatment period for each treatment group should be obtained, and the least squares mean (hereinafter, LSMean), its standard error, and 2-sided 95% CIs for the mean Hb values should be calculated, and the point estimate of the between-group difference (MT-6548 – darbepoetin) of LSMean, its standard error, and 2-sided 95% confidence intervals should be calculated.

## [MMRM Model]

- Covariate: response variable value of the first day of the treatment period
- Fixed effects: treatment group, evaluation time point, interaction of evaluation time point × treatment group
- Degrees of freedom adjustment: Kenward-Roger method
- Covariance matrix within subject for each subject: unstructured (type = UN; unstructured)
 

If the within-subject variance-covariance matrix is not converged using unstructured data, the within-subject variance-covariance matrix should be changed in the following order, and the analysis should be performed using the within-subject variance-covariance matrix that is converged first.

Heterogeneous Toeplitz (TOEPH) → Heterogeneous AR (1) (ARH [1]) → Heterogeneous CS (CSH) → Toeplitz (TOEP) → First-order autoregressive (AR [1]) → Compound symmetry (CS)
- Random effects: subjects

## (2) Hb values at each evaluation time point in the treatment period

## 1) Hb values at each evaluation time point in the treatment period

Hb values and changes in Hb values from the first day of the treatment period at each evaluation time point of the treatment period will be obtained, and their descriptive statistics should be calculated for each treatment group. Before and after comparison should be conducted for changes in Hb values from the first day of the treatment period to each evaluation time point using the paired t-test in the MT-6548 group only.

LSMean, its standard errors, and 2-sided 95% CI for mean Hb values should be calculated in each treatment group using the MMRM (with compound symmetry [CS] for a covariance matrix within subject variance) similar to the analysis used in "(1) mean Hb levels at Week 48 and Week 52 of the treatment period".

Furthermore, LSMean, its standard errors, and 2-sided 95% CI of the change from the first day of the treatment period should be calculated at each evaluation time point of the treatment period in each treatment group using the MMRM.

The time course diagram will be prepared for the mean Hb values at each evaluation time point in the treatment period by treatment group. 95% CI of the mean will be represented by an error bar.

## 2) Analysis by timing of administration of MT-6548 tablets (before meal, after meal, other)

An analysis similar to "1) Hb values at each evaluation time point in the treatment period" should be conducted by the timing of administration of MT-6548 tablets (before meal, after

meal, other). However, this analysis is only for the MT-6548 group; neither tabulation in the darbepoetin group nor comparison with the darbepoetin group is performed.

3) Analysis by previous ESA formulation type

An analysis similar to “1) Hb values at each evaluation time point in the treatment period” should be conducted by the type of previous ESA formulation (epoetin alfa, epoetin beta or epoetin kappa, darbepoetin alfa, epoetin beta pegol). A time course diagram for the mean value is created separately for each treatment group. However, this analysis is only for the MT-6548 group; neither tabulation in the darbepoetin group nor comparison with the darbepoetin group is performed.

4) Analysis by dose of previous ESA formulation types

An analysis similar to “1) Hb values at each evaluation time point in the treatment period” should be conducted for weekly dose of previous ESA formulation (epoetin alfa, epoetin beta or epoetin kappa:  $\geq 4500$  IU,  $< 4500$  IU; other:  $\geq 15$   $\mu$ g,  $< 15$   $\mu$ g; 2 categories) by type of previous ESA formulation (epoetin alfa, epoetin beta or epoetin kappa, darbepoetin alfa, epoetin beta pegol). The number of patients classified by dose was set to be almost equal. The time course diagram of the means should be prepared separately by treatment group. However, this analysis is only for the MT-6548 group; neither tabulation in the darbepoetin group nor comparison with the darbepoetin group is performed.

5) Analysis by Hb value on the first day of the treatment period

An analysis similar to “1) Hb values at each evaluation time point in the treatment period” should be conducted by Hb value on the first day of the treatment period (subjects are divided into 3 categories with equal population). A time course diagram for the mean value is created separately for each treatment group. However, no comparison with baseline of the darbepoetin group or comparison with the darbepoetin group will be conducted.

6) Analysis with or without iron supplements and iron-containing phosphate binders

An analysis similar to “1) Hb values at each evaluation time point in the treatment period” should be conducted for subjects continuously using iron supplements or iron-containing phosphate binders and subjects never using iron supplements and iron-containing phosphate binders during the treatment period. However, subjects who uses intravenous iron at least once should be excluded from the tabulation. Only the MT-6548 group is analyzed.

Since intravenous iron should be included in the tabulation for treatment period phase 1, the tabulation for treatment period phase 1 should be output again.

7) Analysis by iron supplements and iron-containing phosphate binders formulations

An analysis similar to “1) Hb values at each evaluation time point in the treatment period” should be conducted for subjects continuously using iron supplements or iron-containing phosphate binders during the treatment period. However, subjects who uses intravenous iron at least once should be excluded from the tabulation. Only the MT-6548 group is analyzed.

- 8) Analysis by Hb value at Week 52 of the treatment period and CRP levels on the first day of the treatment period

For MT-6548 group only, a scatter plot chart should be provided after linear regression with the following variables.

- x: Logarithmic CRP value on the first day of the treatment period
- y: Hb value at Week 52 of the treatment period

- (3) Proportion of subjects whose Hb level during the treatment period is within the target range (10.0 to <12.0 g/dL) or outside the target range (<10.0 g/dL or  $\geq 12.0$  g/dL)

The number, proportion, and 95% CI (Clopper-Pearson [Exact] method) of subjects with Hb value within the target range (10.0 to <12.0 g/dL, within), <10.0 g/dL (below), and  $\geq 12.0$  g/dL (above) at each time point of the treatment period should be provided by treatment group. For the MT-6548 group, McNemar tests should be used for before and after comparison (ratio of subjects within the target range and out of target range) on the first day and each evaluation time point of the treatment period. The proportion of subjects with Hb value within the target range at each evaluation time point of the treatment period should be provided as a stacked bar chart with the number of subjects in each treatment group as 100%. Stacked bar charts should be generated separately for each treatment group.

### **8.5.2 Analysis of other endpoints**

- (1) Number of days to maintain the target Hb values

The total number of maintenance days from the state meeting the target Hb range to leaving the target Hb range should be calculated for each subject, and the descriptive statistics should be calculated. Only the MT-6548 group is analyzed. However, if treatment period is completed in 52 weeks, the maintenance days should be until Week 52 of the treatment period.

- (2) Proportion of subjects who received rescue therapy with ESA, blood transfusion, or phlebotomy

The number, proportion, and 95% CI (Clopper-Pearson [Exact] method) of the proportion of subjects receiving rescue therapy with an ESA preparation should be provided by treatment group, after the first day of the treatment period, in each period between scheduled study visits and during the entire treatment period from the first day to Week 52 of the treatment period.

The estimate, its 95% CI (exact method), and p-value (Fisher's exact test) for between-group difference (MT-6548 – darbepoetin) should be calculated for the proportion of subjects receiving rescue therapy.

The analyses same to the above subjects receiving rescue therapy with ESA formulation should be performed for subjects receiving rescue therapy with RBC transfusion or receiving phlebotomy.

(3) Study drug dosage

1) Study drug dosage

Descriptive statistics of the mean daily dose of MT-6548 tablets and mean weekly dose of darbepoetin alfa injection (recombinant) should be calculated, after the first day of the treatment period, in each period between scheduled study visits and during the entire treatment period from the first day to Week 52 of the treatment period. The time course diagram for mean daily dose of MT-6548 tablets and mean weekly dose of darbepoetin alfa injection (recombinant) should be separately prepared by treatment group. 95% CI of the mean will be represented by an error bar. Each period between scheduled study visits is defined as the period between the scheduled study visit and the day before the next scheduled study visit.

2) Distribution of MT-6548 tablets and darbepoetin alfa injection

The number, proportion, and 95% CI (Clopper-Pearson [Exact] method) of the proportion per daily dose of MT-6548 tablets and per weekly dose of darbepoetin alfa (recombinant) during the treatment period should be provided by treatment group.

The proportion of subjects receiving each dose of MT-6548 tablets and darbepoetin alfa injection (recombinant) at each evaluation time point of the treatment period should be provided as a stacked bar chart with the number of subjects in each treatment group as 100%. Stacked bar charts should be generated separately for each treatment group.

If no prescription is available on the day of each evaluation time point of the treatment period, the dose should be based on the immediately before prescription.

3) Analysis by timing of administration of MT-6548 tablets (before meal, after meal, other)

An analysis similar to “1) Study drug dosage” should be conducted by the timing of administration of MT-6548 tablets (before meal, after meal, other). Only the MT-6548 group is analyzed.

4) Analysis by previous ESA formulation type

An analysis similar to “1) Study drug dosage” should be conducted by the type of previous ESA formulation (epoetin alfa, epoetin beta or epoetin kappa, darbepoetin alfa, epoetin beta pegol). Only the MT-6548 group is analyzed.

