8.5.3 Rescue therapy

The following rescue therapy options will be provided as needed for subject safety. If any of the following rescue therapies is performed prior to the completion of the scheduled tests at Week 24 of the treatment period, that subject will be withdrawn from the study. If rescue therapies are performed after scheduled tests at Week 24 of the treatment period, the subject can continue in the study unless

investigators/subinvestigators determine study withdrawal is appropriate. Details of any rescue therapy implemented will be recorded in the subject's CRF.

(1) ESA formulations

If a subject has received maximum dosages of MT-6548 Tablets and darbepoetin alfa injection for ≥ 2 weeks and meets all criteria below, the investigator/subinvestigator may administer an ESA as a rescue therapy to improve Hb levels if necessary in order to secure subject safety. An ESA-based rescue therapy may also be provided without meeting the criteria below if the investigator/subinvestigator considers it necessary to secure subject safety, such as in cases of acute decreases in Hb levels. Study drug administration (MT-6548 Tablets and darbepoetin alfa injection) will be discontinued when an ESA-based rescue therapy is provided. Study drug treatment may be resumed after an improvement in Hb levels and should not be coadministered with a rescue therapy with an ESA. Subjects who are not expected to resume study drug treatment will be withdrawn from the study.

Administration of any ESA formulation other than the study drug is considered a rescue therapy. Dosage increase of the study drug darbepoetin alfa injection (including an increase not in accordance with the dosage adjustment algorithm) is not considered a rescue therapy.

- ✓ Anaemia or anaemia symptoms (e.g., fatigue, weakness, shortness of breath, chest pain, confusion, dizziness) become aggravated compared to the first day of the treatment period to the point they are clinically problematic.
- ✓ Hb levels drop to <8.0 g/dL.

(2) RBC transfusion

Usually, RBC transfusions are performed when clinically necessary in instances of acute or major bleeding. For less severe anemia, which may be exacerbated, or moderate to severe anemia symptoms, RBC transfusions may be performed as needed clinically at the discretion of the investigator/subinvestigator.

(3) Phlebotomy

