12.1 Withdrawal criteria

Subjects will be withdrawn from the study if the following criteria are met:

- (1) If the subject expresses a desire to withdraw from the study.
- (2) If it is discovered that the subject is clearly ineligible for study participation.
- (3) If investigators/subinvestigators determine that AEs make continued participation in the study difficult.
- (4) If the subject meets one of the following criteria regarding hepatic function abnormalities during the study.

- 1) ALT or AST > 3x ULN and total bilirubin > 2x ULN
- 2) ALT or AST > 3x ULN and INR > 1.5*¹
- 3) ALT or AST > 8x ULN
- 4) ALT or AST remains > 5x ULN over 2 weeks*²
- 5) ALT or AST > 3x ULN with symptoms including e.g., fatigue, nausea, vomiting, right upper quadrant pain, fever, rash or eosinophilia

*¹: The subject should be withdrawn from the study if the measurement of PT-INR is performed besides this study and the value meets the criterion.

*²: Administration of the study drug should be avoided with ALT or AST > 5x ULN unless there are no other good therapeutic options.

- (5) If rescue therapy is performed prior to conclusion of scheduled tests at Week 24.
- (6) If investigators/subinvestigators determine that continuation of the study is inappropriate for a subject, such as if hyperviscosity syndrome occurs or if control of Hb within the target range is impossible.
- (7) If the subject no longer requires hemodialysis or hemodiafiltration
- (8) If the subject has undergone renal transplantation
- (9) If pregnancy of the subject is discovered.
- (10) If the investigator/subinvestigator determines a subject should withdraw from the study for any other reason.

Rationale

- (1) Set out of ethical considerations.

- (2) (7) (8) Set in order to prevent study drug administration to subjects unsuitable for inclusion in safety or efficacy evaluation.
- (3) (4) (6) (9) Set out of safety considerations.
- (5) Set because evaluating efficacy of MT-6548 accurately would be difficult.
- (10) Set in order to allow the investigator/subinvestigator to make determinations regarding study continuation for significant safety-related reasons other than those enumerated above.

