### 8.5.3 Analysis of other endpoints

- (1) Number of days to maintain the target Hb values

The number of maintenance days from the state meeting the target Hb range to leaving the target Hb range should be calculated for each subject. The total number of maintenance days should be calculated for each subject, and the descriptive statistics should be calculated. Only the MT-6548 group is analyzed. However, if treatment period is completed in 24 weeks, the maintenance days should be until Week 24 of the treatment period.

- (2) Proportion of subjects who received rescue therapy with ESA, blood transfusion, or phlebotomy

The number, proportion, and 95% CI (Clopper-Pearson [Exact] method) of the proportion of subjects receiving rescue therapy with an ESA preparation should be provided by treatment group, after the first day of the treatment period, in each period between scheduled study visits and during the entire treatment period from the first day to Week 24 of the treatment period.

The estimate, its 95% CI (exact method), and p-value (Fisher's exact test) for between-group difference (MT-6548 – darbepoetin) should be calculated for the proportion of subjects receiving rescue therapy.

The analyses same to the above subjects receiving rescue therapy with ESA formulation should be performed for subjects receiving rescue therapy with RBC transfusion or receiving phlebotomy.

(3) Study drug dosage

1) Study drug dosage

Descriptive statistics of the mean daily dose of MT-6548 tablets and mean weekly dose of darbepoetin alfa injection should be calculated, after the first day of the treatment period, in each period between scheduled study visits and during the entire treatment period from the first day to Week 24 of the treatment period. The time course diagram for mean daily dose of MT-6548 tablets and mean weekly dose of darbepoetin alfa injection should be separately prepared by treatment group. 95% CI of the mean will be represented by an error bar. Each period between scheduled study visits is defined as the period between the scheduled study visit and the day before the next scheduled study visit.

2) Distribution of MT-6548 tablets and darbepoetin alfa injection

The number, proportion, and 95% CI (Clopper-Pearson [Exact] method) of the proportion per daily dose of MT-6548 tablets and per weekly dose of darbepoetin alfa during the treatment period should be provided by treatment group.

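### Days in the target Hb range is an undivided total for the MT-6548 arm only, with no counting rule for subjects who discontinue

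*SAP*

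**What the plan says.** Final SAP 8.5.2 (1) defines the measure: "The total number of maintenance days from the state meeting the target Hb range to leaving the target Hb range should be calculated for each" (of the subjects). It then summarises the totals descriptively and adds: "Only the MT-6548 group is analyzed". The only statement of where counting stops concerns completers: "However, if treatment period is completed in 52 weeks, the maintenance days should be until Week 52 of the treatment period". The section gives no denominator, no rule for subjects who discontinue, and no darbepoetin value.

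Phase 1 SAP 8.5.3 (1) does the same over 24 weeks: "The total number of maintenance days should be calculated for each subject, and the descriptive statistics should be calculated. Only the MT-6548 group is analyzed".

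Four other places bear on it:

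- Under Protocol 8.5.3, if rescue is given "prior to the completion of the scheduled tests at Week 24 of the treatment period, that subject will be withdrawn from the study". Protocol 12.1 repeats this and also lists withdrawal for adverse events, transplantation, inability to keep Hb in range, and other reasons.
- SAP 7.3 drops efficacy data from the day after rescue.
- SAP 7.1 makes a derived variable missing if any value needed to derive it is missing.
- Protocol 13.3.2 (3) has continuous other endpoints described by treatment group. Section 10 of each SAP declares no change from the protocol.

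**The concern.** Observation time differs between subjects. Some leave early, some of them because of rescue, and a subject rescued after Week 24 who stays in the study contributes no further efficacy data. A sum of days in range that is not related to the days observed therefore carries two things at once: how well Hb was held, and how long the subject was followed. A reader who sees the mean number of days cannot separate them.

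The second gap is the comparator. Hb is sampled on the same schedule in both arms (Protocol 9.2.3), yet this measure is produced for one arm. The reader has no darbepoetin figure against which to judge it.

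What is at stake is the descriptive reading of one exploratory endpoint.

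**Working it through.** **The plan's own figure.** No figure is stated for days in range. The only stated probability is the one above 95% for the primary analysis (SAP 2.4), and its non-inferiority part reproduces: 0.75 / (1.73 × √(2/150)) = 0.75 / 0.1998 = 3.754; 3.754 − 1.960 = 1.794; power 96.4%. Requiring the MT-6548 interval to lie inside 10.0–12.0 g/dL leaves it at about 96.3% by simulation. Nothing below changes this.

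**Inputs.** Scheduled follow-up is 364 days to Week 52 and 168 days to Week 24 (Protocol Table 9.1-1). The documents give neither a discontinuation rate *d*, nor the mean follow-up *m* of discontinuers, nor the fraction of time in range *f*. These are assumptions and are shown as ranges.

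**Reading A: discontinuers are counted to discontinuation.** This is the natural reading, because the total is to be calculated for every subject and a cut-off is named only for completers.

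For one subject, total = *f* × days observed, so the maximum equals the days observed:

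- Week 12: 12 × 7 = 84 days. A completer reaches 84 days when in range 84/364 = 23.1% of the time.
- Week 24: 24 × 7 = 168 days. A completer reaches this at 168/364 = 46.2%.
- A completer in range 30% of the time scores 0.30 × 364 = 109 days. That is more than the 84 days of a subject always in range who left at Week 12.
- In the Phase 1 analysis, the same Week 12 leaver has 84 of a possible 168 days, or 50%.

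For a group with the same *f* in every subject:

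mean total = *f* × [(1 − *d*) × 364 + *d* × *m*]

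relative fall against full follow-up = *d* × (1 − *m*/364), which does not depend on *f*

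| *d* | Fall if *m* = 182 days | Fall if *m* = 84 days |
|---|---|---|
| 5% | 2.5% | 3.8% |
| 10% | 5.0% | 7.7% |
| 20% | 10.0% | 15.4% |
| 30% | 15.0% | 23.1% |

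For example, with *f* = 0.75 the mean is 0.75 × 364 = 273.0 days with no discontinuation. With 20% leaving at a mean of 182 days it is 0.75 × (0.8 × 364 + 0.2 × 182) = 245.7 days. Hb control is identical in the two cases.

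**Reading B: SAP 7.1 applies.** Subjects lacking the later Hb values have no derived value. The follow-up effect then disappears, but the summary describes only subjects with complete data. Anyone withdrawn because of rescue or loss of Hb control is absent from it.

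**What a percentage does, and what it hides.** Days in range divided by days observed gives the Week 12 leaver 84/84 = 100% and the 30% completer 30%, so length of follow-up no longer enters. However, if that Week 12 subject left because rescue was given, 100% conceals a failure. Counting the remaining 280 scheduled days (364 − 84) as out of range gives 84/364 = 23.1%. The two versions answer different questions.

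**The case against.** Much of the case on the other side stands.

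- *A reader might infer that the plan scores early withdrawal as poor control.* The SAP does not say so. It is silent on discontinuers, and 7.1 could remove them. Each reading has a defect, but the text does not settle which one applies.
- *A reader might infer that longer follow-up is rewarded generally.* Completers are all cut at Week 52 and differ only by the visit window, Day 357 to Day 371, which is 14 days. The effect lies between completers and discontinuers.
- *A reader might infer that the trial cannot compare maintenance between arms.* It can. The repeated-measures model compares mean Hb at Weeks 20 and 24 and at Weeks 48 and 52. The proportions within, below and above target are tabulated by visit in both arms with exact intervals. The overall between-arm difference in those proportions was struck from the Phase 1 SAP by erratum and is absent from the final SAP, so they stand side by side. Only the days measure lacks a darbepoetin figure.
- *A reader might infer a breach of the protocol.* Days in range is not on the protocol's endpoint list; the SAPs added it. Protocol 13.3.2 (3) is a general rule for other endpoints, so the one-arm restriction is out of line with it and is not explained. The SAPs restrict several other descriptive analyses to MT-6548 in the same way.
- *Subjects withdrawn for rescue or lost Hb control arguably should lose days.* This is a fair point, and it is why a percentage of observed time cannot simply replace the total.
- *The protocol links maintenance after switching to the 24-week Phase 1.* The 52-week duration is set for long-term safety, so the 52-week version carries less weight for that purpose.

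**Conclusion.** The point holds as a low-cost improvement. As written, the measure has no denominator, no comparator value and no stated handling of discontinuers. If discontinuers are counted to discontinuation, the mean total falls by 2.5% to 15% with no change in Hb control, assuming 5% to 30% discontinue after a mean of 182 days. The fall is 3.8% to 23.1% if they all leave at Week 12. These ranges assume the same fraction of time in range in leavers and completers. That is unlikely to be exact, because some withdrawals are driven by Hb. If discontinuers are set to missing, the defect is selection.

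Phase 1 SAP 8.5.4.7 treats the other endpoints as exploratory. The primary non-inferiority conclusion, the error rate and the sample size are not affected, and the documents support no stronger claim.

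**What to change.** In final SAP 8.5.2 (1) and Phase 1 SAP 8.5.3 (1):

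1. State how subjects who discontinue, and those with data cut by rescue, are counted, and whether 7.1 applies to this measure.
2. Calculate the measure in both arms.
3. Report total days and also the percentage of observed time in range: days in range divided by days from first dose to the last Hb used for efficacy, with numerator and denominator over the same interval. Give the MT-6548 minus darbepoetin difference and its 95% CI, labelled descriptive.
4. Add a version in which the remaining scheduled days of subjects withdrawn for rescue or loss of Hb control count as out of range, so that the percentage does not hide those failures.
5. State how the days between two visits are assigned, since any days measure needs this.

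The cost is SAP wording, a rerun of the same program on the second arm, and a few extra exploratory table lines. No new data are needed.
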